5. To evaluate the proportion of HCV RNA positive participants who initiate HCV treatment at 12 months (52 weeks) following HCV RNA testing.
6. To evaluate the proportion of participants who complete HCV direct-acting antiviral (DAA) treatment following point-of-care HCV antibody testing with reflex HCV RNA testing in those who are HCV antibody detectable who received HCV treatment;
7. To evaluate the proportion of participants who achieve an SVR (defined as HCV RNA below the lower limit of quantitation at post treatment week 12) following point-of-care HCV antibody testing with reflex HCV RNA testing in those who are HCV antibody detectable who received HCV treatment.
8. To evaluate the proportion of participants who are HCV RNA negative at 12 months (52 weeks) following HCV RNA testing.
9. To evaluate the cost-effectiveness of this testing strategy.

4. Participant population

Participants will be included from settings that provide services to people with a risk factor for the acquisition of HCV infection, including drug treatment clinics, needle and syringe programs, prisons, mobile outreach services, community health services, mental health services, homelessness services, and other appropriate settings nationally. It is anticipated approximately 40,000 participants will be screened for HCV infection using point-of-care HCV testing.

Inclusion criteria

Participants are eligible for inclusion if the following criteria are met:

- a. Provide informed consent
- b. ≥ 18 years of age.

Exclusion criteria

- b. Is unable or unwilling to provide informed consent

5. Study design

This is an observational cohort study. Participants will attend a single visit where they will provide informed consent and receive point-of-care HCV testing. All other study procedures will comprise data collection only.

Participants will be offered treatment as standard of care. Participants who are HCV RNA detectable will also be linked to standard of care for any other clinical assessments and treatment

initiation, and local health staff may provide counselling and medical advice for these tests, and link participants with support services available in their state or territory.

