8.2 Sample size

Overall, 40,000 point-of-care HCV tests will be performed in different settings as part of the Australian National HCV Point-of-care Testing Program. It is estimated that the HCV prevalence will be 15% (n=6,000 people who are HCV RNA detectable) and the treatment uptake following testing will be 65% (n=3,900). Under these assumptions, the 95% confidence intervals around the estimate for HCV treatment uptake will be 64.0%-66.0% and for HCV RNA prevalence will be 14.7%-15.4%. For analyses evaluating factors associated with HCV treatment uptake, we will have 90% power to detect an odds ratio of 1.20 or greater ($\alpha=0.05$) for a variable that is 50% prevalent (i.e. recent injecting drug use).

Analysis will follow the STROBE guidelines for observational studies. The analysis of the primary outcome will occur when all patients have completed 12 weeks of follow-up (from enrolment) or have been permanently lost to follow-up. Participant flow will be summarised, showing the numbers of participants included. The primary endpoint will be the proportion of participants who initiate HCV treatment within 12 weeks of HCV RNA testing. The secondary endpoints will be:

- Proportion of people who accept point-of-care testing among those offered testing.
- Proportion of people who are HCV RNA detectable among people tested.
- Time to HCV treatment uptake following finger-stick point-of-care HCV antibody testing with reflex HCV RNA testing among people who receive treatment.
- Proportion of HCV RNA detectable participants who initiate HCV DAA treatment at 12 months (52 weeks) following enrolment.
- Proportion of participants who complete HCV direct-acting antiviral (DAA) treatment.
- Proportion of participants who achieve an SVR (defined as HCV RNA below the lower limit of quantitation at post treatment week 12).
- To evaluate the proportion of HCV RNA detectable participants who are HCV RNA negative at 12 months (52 weeks) following finger-stick point-of-care HCV antibody testing with reflex HCV RNA testing.
- Cost-effectiveness of different testing strategies.

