Participant characteristics at baseline will be summarised. Factors hypothesised to be associated with treatment initiation within 12 weeks of testing will be determined *a priori* and will include age, gender, Aboriginal and Torres Strait Islander status, and geography. Logistic regression will be used to assess factors associated with treatment initiation. Secondary analyses will be performed on these outcomes with stratified analyses performed where possible.

A detailed statistical analysis plan will be developed towards completion of the study, and prior to analyses being performed.

9. Data collection, source documents and record retention

The Principal Investigator and the institution where the study will be conducted will permit study-related monitoring, audits and ethics committee review providing direct access to source documents. Flinders University, NSW Pathology (NSW study sites) and Cepheid may also request to conduct an audit or inspection at sites. Prior to this they would seek permission from the site to access study related records physically at site.

Data will be collected on study specific electronic or paper copy case record forms. The Principal Investigator is responsible for ensuring the data collected are complete, accurate and recorded in a timely manner.

Data will be collected in a de-identified format and submitted to the Kirby. All data will be stored in the secure study database, RedCap, and will be kept on a secure password protected server hosted by UNSW Sydney, until its destruction. Only approved site staff and study staff, will have access to this data. Site staff will be responsible for collecting and entering the data for their site, and will only have access to the study data collected at their own site.

De-identified data collected from this research project may be used in future research projects following separate review and approval from a Human Research Ethics Committee (HREC).

The informed consent forms will be stored at site level according to the site's local process, and in accordance with ICH-GCP guidelines. Archiving and subsequent secure destruction of the informed consent forms and other study specific documents at site level are the responsibility of the Principal Investigator. When the period for archiving has elapsed, sites will be notified by the Sponsor, UNSW Sydney, to securely destroy the documents in accordance with ICH-GCP guidelines.

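### Section 8.2's precision and power figures ignore clustering by site, and the printed 95% uptake interval is too narrow even for independent participants

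*Protocol*

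**What the plan says.** Protocol section 8.2 states: "Overall, 40,000 point-of-care HCV tests will be performed in different settings". It takes 15% of these as RNA-detectable (6,000 people) and 65% of those as treated (3,900 people). It then says "the 95% confidence intervals around the estimate for HCV treatment uptake will be 64.0%-66.0" percent, gives a matching interval for prevalence ("for HCV RNA prevalence will be 14.7%-15.4" percent), and claims 90% power at alpha 0.05 for an odds ratio of 1.20 on a variable with 50% prevalence. Its example of such a variable is recent injecting drug use. The Statistics row of the synopsis repeats all these figures.

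The analysis text at the end of 8.2 says "Logistic regression will be used to assess factors associated with treatment initiation". The a priori factors "will include age, gender, Aboriginal and Torres Strait Islander status, and geography". The same text foresees stratified analyses where possible and defers detail to a later statistical analysis plan.

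Section 4 recruits from "drug treatment clinics, needle and syringe programs, prisons, mobile outreach services, community health services", plus mental health, homelessness and other services. Under sections 5 and 6 the study prescribes no treatment; RNA-detectable participants are linked to standard care. No section gives a number of sites, an ICC or a design effect.

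**The concern.** The primary outcome is whether a person starts treatment within 12 weeks. The study does not deliver treatment, so this depends partly on how well each service links people to care. People tested at the same site are then likely to have correlated outcomes, and 6,000 people carry less information than 6,000 independent observations. The planning figures in 8.2 make no allowance for this.

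Two results are exposed. The first is the primary interval. Section 2 hypothesises uptake above 65%, so its width decides whether an estimate a little above 65% supports the hypothesis. The second is inference on factors largely fixed within a site. Geography is one of the four named factors and is the likely case: standard errors that ignore site would be too small for it.

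Service setting, which defines the recruitment frame, is not among the named factors. If uptake and participant mix both differ by setting, person-level odds ratios could partly reflect the service.

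**Working it through.** **Inputs from section 8.2:** n = 6,000; uptake p = 0.65; odds ratio 1.20; factor prevalence 50%; alpha 0.05 (sidedness not stated, two-sided assumed).

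**Assumed, because the documents give none:** 100 sites of equal size, so m = 6,000/100 = 60 RNA-detectable people per site; ICC 0.01 to 0.05.

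**1. The printed uptake interval.** SE = √(0.65 × 0.35 / 6,000) = 0.00616.
- 95%: 1.96 × 0.00616 = 0.0121, giving 63.8% to 66.2%. Wald, Wilson, Clopper-Pearson and Agresti-Coull limits agree to one decimal.
- 90%: 1.645 × 0.00616 = 0.0101, giving 64.0% to 66.0%, the printed limits.
- A 95% half-width of 1.0 point would need 1.96² × 0.65 × 0.35 / 0.01² ≈ 8,740 people.

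The prevalence interval in the same sentence does reproduce at 95%: the Wilson limits for 15% of 40,000 are 14.65% to 15.35%, printed as 14.7% to 15.4%.

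**2. The printed power.** An odds ratio of 1.20 with average uptake 65% means 62.9% against 67.1%. With 3,000 per group and a two-sided two-proportion test, power is 92.0%. Taking 65% as the unexposed rate gives 91.3%; as the exposed rate, 92.7%. The 90% claim is sound, but every version treats participants as independent.

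**3. Allowing for site (illustration).** Design effect DE = 1 + (m − 1) × ICC. Interval half-width = 1.96 × 0.00616 × √DE. For a factor fixed within site, the power calculation uses 3,000/DE per group.

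| ICC | DE | Effective n | Uptake 95% interval | Power, site-level factor, OR 1.20 |
|---|---|---|---|---|
| 0 | 1.00 | 6,000 | 63.8%-66.2% | 92% |
| 0.01 | 1 + 59 × 0.01 = 1.59 | 3,774 | 63.5%-66.5% | 76% |
| 0.02 | 1 + 59 × 0.02 = 2.18 | 2,752 | 63.2%-66.8% | 63% |
| 0.05 | 1 + 59 × 0.05 = 3.95 | 1,519 | 62.6%-67.4% | 39% |

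The last column does not apply to factors that vary mainly within sites.

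**4. Bearing on the hypothesis (illustration).** Suppose 67% of 6,000 start treatment. The half-width under independence is 1.96 × √(0.67 × 0.33 / 6,000) = 1.19 points, so the lower limit is 65.8%. At DE 3.95 it is 67 − 1.19 × √3.95 = 64.6%. The lower limit drops below 65% once DE exceeds (2/1.19)² ≈ 2.8.

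**5. Confounding by setting (illustration).** Take two equal settings with 75% and 55% uptake, a factor present in 60% and 40% of their participants, and no effect of the factor within either. Crude uptake is 0.6 × 75 + 0.4 × 55 = 67% with the factor and 0.4 × 75 + 0.6 × 55 = 63% without. The crude odds ratio is (67/33)/(63/37) = 1.19, about the size the study is powered to detect.

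**The case against.** The strongest objection is that standard-error method, random effects and the final covariate set are ordinary content of the statistical analysis plan, which the protocol defers and which is not at hand. This largely stands for the model. A reader might infer that the protocol fixes an ordinary logistic model without site or setting. It does not: the sentence names a model family that a GEE or random-intercept model also fits, the factor list is open, and stratified analyses are foreseen. The objection does not reach the interval and power in 8.2, which are the protocol's own figures.

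A second objection is that the inflated interval presumes inference beyond the participating sites. If the sites are treated as fixed, ICC inflation of the overall proportion does not apply. That is a legitimate choice of target. However, section 2 words its hypothesis for people at increased risk generally, which points to the wider target, and the protocol does not state the narrower one.

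A third is that the power example in 8.2 is a person-level variable, to which the full design effect does not apply. This stands. A reader might infer that the power is overstated for every factor; age, gender and Aboriginal and Torres Strait Islander status vary within sites, and for them the figure is roughly right. Geography is not defined in the protocol, so treating it as fixed within a site is itself an inference, and mobile outreach may be an exception.

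**Conclusion.** The point holds for the planning figures. The printed uptake interval is wrong without any assumption about clustering: it should read 63.8% to 66.2%. Clustering is a separate matter and does not explain the printed limits.

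The direction of the clustering effect is certain for any positive within-site correlation, given inference beyond the sampled sites. Its size is not known. The figures of 1.6 to 4.0 for the design effect and 76% to 39% for power rest wholly on an assumed 100 equal sites and ICCs of 0.01 to 0.05. Fewer sites, larger ICCs or unequal site sizes would make it worse; more sites or a smaller ICC would make it milder.

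A reader might also infer that the factor effects are confounded by service type. The documents do not show this: no figure compares uptake or participant mix between settings, and the stated aim is association. Confounding by setting is a risk worth guarding against.

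**What to change.** In section 8.2 and the synopsis, correct the uptake interval to 63.8% to 66.2%. State that the interval and the power assume independent participants. Give the expected number of sites and a plausible ICC range, show both figures over the resulting design effects, and say that the power loss applies to site-level factors.

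In the analysis text of 8.2, specify site-clustered standard errors (robust/GEE or random intercept) for the primary interval and the logistic model, and add service setting to the a priori factors.

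This changes wording and analysis only. Site staff enter data for their own site (section 9), so site is known and setting follows from it; no new data are needed. The downside is a wider, less favourable interval.

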10.1 Submission of data

Electronic CRFs: Following each participant HCV test or medical record review, the designated site staff will complete the visit specific CRF. Once all required information is received the CRF shall

be considered complete. Project Team staff will then monitor the data for completeness and accuracy. Any CRF discrepancies, either manual or automatic, will be addressed with the site staff for clarification.

The site Principal Investigator is responsible for ensuring the completion of accurate source documentation to support data collected on case report forms.

It is not acceptable for the CRF to be the only record of study participation and progress must also be recorded in each participant's medical record. This is to ensure that anyone accessing the medical record has adequate knowledge that the participant is a clinical trial participant.

Any document that acts as a source document (the point of the initial recording of a piece of data) should have evidence of who the person recording or reviewing the data is. Persons completing the source documents must be listed as a site staff member.

The sponsor's monitor might visit sites to conduct monitoring. Flinders and/or Cepheid may also visit the sites to access study related documents.

The Principal Investigator is responsible for retaining all essential documents listed in ICH Good Clinical Practice guidelines. These must be organised in a comprehensive filing system that is accessible to study monitors and other relevant personnel.

10.2 Archiving

The Principal Investigator is responsible for ensuring all study documents are retained for a minimum of 7 years or as per local site guidelines, whichever is longer, following completion and publication of the study.

11. Ethics committee/regulatory approval

The sponsor is responsible for ensuring regulatory approval for the study is obtained where required.

The site Principal Investigator is responsible for obtaining IRB/EC approval for the protocol in compliance with local regulatory requirements prior to entering any participant into the study. The approval letter/document must clearly identify the protocol and all documents approved by the IRB/IEC including version number & date of the protocol. A copy of the approval document must be sent to the study sponsor.

The site Principal Investigator must also obtain approval for any amendments to the protocol. The Principal Investigator must comply with all IRB/IEC reporting requirements for all adverse events,

annual updates and end of study reports and must agree to abide by any IRB/IEC conditions of approval.

The site Principal Investigator (or designee) is responsible for ensuring freely-given consent is obtained from each potential participant prior to the conduct of any protocol-specific procedures. The Principal Investigator may delegate the task of obtaining consent to appropriately qualified Sub-investigator(s).

Consent for this study will occur either via hardcopy or verbal consent, depending on the site/participant preference. If hardcopy, the participant will date and sign the participant information and consent form together with the date and signature of the person conducting the consent discussion. If verbal consent is utilised the person conducting the consent will sign the verbal consent form to confirm that the study has been explained to the participant and consent has been given.

For hardcopy consent, if the participant is illiterate, an impartial witness should be present during the entire consent discussion. Once the discussion is complete, the participant must sign and date the informed consent form, if capable. The impartial witness must also sign and date the consent form along with the person who conducted the consent discussion.

A copy of the participant information and consent form will be offered to the participant, either hardcopy or electronic copy (via email or SMS) to keep. The participant must be informed in a timely manner of any new information that becomes available during the course of the study that may affect their willingness to continue study participation.

This study shall be conducted in accordance with the ethical principles laid out in the Declaration of Helsinki (most current issued version) and the National Statement on Ethical Conduct in Research Involving Humans (most current issued version).

12. Confidentiality of data

By signing the Clinical Trial Agreement, the site Principal Investigator affirms to the sponsor that information provided to them by the sponsor will be maintained in confidence and divulged only as necessary to the ethics committee and institution employees directly involved in the study. Both ethics committee members and employees must also understand the confidentiality requirements for any information divulged to them. The data generated by this study will be considered confidential, except where it is included in a publication as agreed in the publication policy of this protocol.

All patient data will be stored in a de-identified form and individuals will only be identified by a study number and age. Data will be stored in a secure location for a minimum of 7 years, or as per local site guidelines, whichever is longer.

Data confidentiality will be maintained at all times and no documents containing the participating institution's name or other identifying information will be made publicly available.

13. Governance

The study is sponsored by UNSW and coordinated through the Kirby Institute. It is funded by the Commonwealth Government, the National Health and Medical Research Council, and NSW Health. The Kirby Institute has established governance and implementation structures which use resources efficiently to deliver program objectives on schedule.

14. Quality Control (QC) and Quality Assurance (QA)

The sponsor agrees to be responsible for implementing and maintaining quality control and quality assurance systems with written standard operating procedures to ensure the study is conducted and data are generated, documented and reported in compliance with the protocol, Good Clinical Practice standards and all applicable local laws and regulations relating to the conduct of a clinical trial.

15. Publication Policy

